6.4.3 Early Termination Visit (if needed)

The following activities will be performed at the early termination visit on subjects who withdraw, or are withdrawn or terminated from this trial:

- Interim medical history, including an assessment for new medical conditions and symptoms suggestive of PIMMCs, will be obtained by interview of subjects and any changes since the previous clinic visit or contact will be noted.
- Memory Aid information will be reviewed with subjects (if within 7 days after the last study vaccination).
- All concomitant medications will be recorded on the appropriate data collection form (if within 180 days after the last study vaccination, including those that are experimental, what type (inactivated or live attenuated), what subtype (e.g., A/H3, A/H5, A/H9) and approximate date of vaccination will be recorded on the appropriate DCF, if known and not previously collected). Receipt of any non-study influenza vaccine will be recorded if within 180 days after the last study vaccination.
- Unsolicited non-serious AEs will be documented and reported from the time of each study vaccination through approximately 21 days after each study vaccination. SAEs, MAAEs, including NOCMCs, and PIMMCs will be documented and reported from the time of the first study vaccination through approximately 12 months after last study vaccination).
- Vital signs, including oral temperature, pulse, and blood pressure, may be obtained if indicated. Subjects must not eat or drink anything hot or cold, or smoke within 10 minutes prior to taking oral temperature.
- A targeted physical examination, including an assessment for signs suggestive of PIMMCs, may be performed, if indicated based on review of interim medical history, by a study clinician licensed to make medical diagnoses and listed on the Form FDA 1572 as the site PI or sub-investigator.
- The study vaccination site will be examined (if within 7 days after the last study vaccination).
- Post-administration reactogenicity assessments will be performed (if within 7 days after the last study vaccination).
- Approximately 10 mL of venous blood will be collected for serum antibody assays (if within 21 days after the last study vaccination).
- Approximately 10 mL of venous blood will be collected for clinical safety labs (WBC, Hgb, PLT, ALT, T. Bili, and Cr), and performed by the central (clinical) laboratory if done within 7 days after the last study vaccination.

- Approximately 10 mL of venous blood will be collected for future research (if within 21 days after the last study vaccination) from subjects who consent to collection of serum for future use either by signing an ICF that includes collection of future use samples as a condition of study participation or by indicating that they can opt in to sample collection for future use if the ICF allows the option to choose that option.

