- Subjects will be provided with a Memory Aid and other study-related materials to record daily oral temperature, solicited injection site and systemic reactions, any unsolicited AEs, and concomitant medications. Subjects will be encouraged to take their oral temperature around the same time each day. Subjects must not eat or drink anything hot or cold, or smoke within 10 minutes prior to taking oral temperature. Subjects will be instructed on how to use their Memory Aid and how to measure and record AEs prior to discharge from the clinic. Subjects will be instructed to notify the study center if they develop any severe reactions after the second study vaccination. If the site PI or appropriate sub-investigator deems the reaction severe enough, further instructions will be given to the subject on the proper course of action, including a return to the clinic for immediate evaluation if appropriate.

Visit 05, Day 25, Memory Aid Review, Phone Call
(Window: Day 4 ±1 days post second study vaccination)

Study personnel will contact subjects by phone to solicit any AE/SAE, medical history, and concomitant medication information (including solicitation for receipt of any non-study influenza vaccines), including those that are experimental, what type (inactivated or live attenuated), what subtype (e.g., A/H3, A/H5, A/H9) and approximate date of vaccination will be recorded on the appropriate DCF, if known and not previously collected) and review information on their Memory Aid. Based on the information, subjects may be asked to return to the clinic for evaluation. Note: For subjects who are discontinued from the receipt of the second study vaccination, AEs will be limited to SAEs, MAAEs, including NOCMCs, and PIMMCs.

Visit 06, Day 29, Clinic Visit
(Window: Day 8±2 days post second study vaccination)

- Interim medical history, including an assessment for new medical conditions, stability of chronic diseases, and symptoms suggestive of PIMMCs, will be obtained by interview of subjects and any changes since the previous clinic visit or contact will be noted.

- Memory Aid information will be reviewed with subjects.
- All concomitant medications (including solicitation for receipt of any non-study influenza vaccines), including those that are experimental, what type (inactivated or live attenuated), what subtype (e.g., A/H3, A/H5, A/H9) and approximate date of vaccination will be recorded on the appropriate DCF, if known and not previously collected).

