- All AE/SAEs will be recorded on the appropriate data collection form. Note: for subjects who discontinued from the receipt of the second study vaccination, AEs will be limited to SAEs, MAAEs, including NOCMCs, and PIMMCs.
- A targeted physical examination, including an assessment for signs suggestive of PIMMCs, may be performed, if indicated based on review of interim medical history, by a study clinician licensed to make medical diagnoses and listed on the Form FDA 1572 as the site PI or sub-investigator.
- The second study vaccination site will be examined.
- Approximately 10 mL of venous blood will be collected for clinical safety labs (WBC, Hgb, PLT, ALT, T. Bili, and Cr), and performed by the central (clinical) laboratory.
- Approximately 10 mL of venous blood will be collected for serum antibody assays.
- Approximately 10 mL of venous blood will be collected for future research from subjects who consent to collection of serum for future use either by signing an ICF that includes collection of future use samples as a condition of study participation or by indicating that they can opt in to sample collection for future use if the ICF allows the option to choose that option.

Visit 07, Day 43, Clinic Visit

(Window: Day 22+7 days post second study vaccination)

- Interim medical history, including an assessment for new medical conditions, stability of chronic diseases, and symptoms suggestive of PIMMCs, will be obtained by interview of subjects and any changes since the previous clinic visit or contact will be noted.
- All concomitant medications (including solicitation for receipt of any non-study influenza vaccines), including those that are experimental, what type (inactivated or live attenuated), what subtype (e.g., A/H3, A/H5, A/H9) and approximate date of vaccination will be recorded on the appropriate DCF, if known and not previously collected).

- All AE/SAEs will be recorded on the appropriate data collection form. Note: for subjects who discontinued from the receipt of the second study vaccination, AEs will be limited to SAEs, MAAEs, including NOCMCs, and PIMMCs.
- A targeted physical examination, including an assessment for signs suggestive of PIMMCs, may be performed, if indicated based on review of interim medical history, by a study clinician licensed to make medical diagnoses and listed on the Form FDA 1572 as the site PI or sub-investigator.
- Approximately 10 mL of venous blood will be collected for serum antibody assays.

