- Approximately 10 mL of venous blood will be collected for future research from subjects who consent to collection of serum for future use either by signing an ICF that includes collection of future use samples as a condition of study participation or by indicating that they can opt in to sample collection for future use if the ICF allows the option to choose that option.

Visit 08, Day 82, Safety Follow-up, Phone Call
(Window: Day 61±7 days post second study vaccination)

Subjects will be contacted by phone to query for safety events and solicitation for receipt of all concomitant medications (including any solicitation for receipt of any non-study influenza vaccines), including those that are experimental, what type (inactivated or live attenuated), what subtype (e.g., A/H3, A/H5, A/H9) and approximate date of vaccination will be recorded on the appropriate DCF, if known and not previously collected. Adverse events limited to MAAEs including NOCMCs, PIMMCs, and SAEs that have occurred since the previous clinic visit or contact will be solicited. Based on the information, subjects may be asked to return to the clinic for evaluation.

Visit 09, Day 142, Safety Follow-up, Phone Call
(Window: Day 121±14 days post second study vaccination)

Subjects will be contacted by phone to query for safety events and solicitation for receipt of all concomitant medications (including any solicitation for receipt of any non-study influenza vaccines), including those that are experimental, what type (inactivated or live attenuated), what subtype (e.g., A/H3, A/H5, A/H9) and approximate date of vaccination will be recorded on the appropriate DCF, if known and not previously collected. Adverse events limited to MAAEs including NOCMCs, PIMMCs, and SAEs that have occurred since the previous clinic visit or contact will be solicited. Based on the information, subjects may be asked to return to the clinic for evaluation.

Visit 10, Day 202, Safety Follow-up, Clinic Visit (Window: Day 181±14 days post second study vaccination)

- Interim medical history, including an assessment for new medical conditions, stability of chronic medical diseases, and symptoms suggestive of PIMMCs, will be obtained by interview of subjects and any changes since the previous clinic visit or contact will be noted.

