APPENDIX A: SCHEDULE OF PROCEDURES AND EVALUATIONS

Study Visit	V00	V01	V02	V03	V04	V05	V06	V07	V08	V09	V10	V11	Early Term	Unscheduled
Study Day Post 1st Vaccination	Screen Optional D-28 to -1	Dose 1 D1	D4 ±1d	D8 +2d	D22 +7d	D25	D29	D43	D82	D142	D202	D387		
Study Day Post 2nd Vaccination					Dose 2 D1	D4 ±1d	D8 +2d	D22 +7d	D61 ±7d	D121 ±14d	D181 ±14d	D366 ±14d		
Obtain Informed Consent	X [∞]	X ^{∞-1}												
Collect Demographic Information	X	X ^{†*}												
Review Eligibility Criteria	X	X ^{†-1}			X [†]									
Medical History [@]	X	X ^{†-1}	X	X	X [†]	X	X	X			X		X	X(if indicated)
Concomitant Medications ⁵	X	X ^{†-1}	X	X	X [†]	X	X	X	X	X	X		X (if within 180 days after last study vaccination)	X (if prior to 180 days after last study vaccination)
Vital Signs ⁵ (Oral Temperature [°] , Pulse, and BP)	X	X [†]			X ^{†2}								X (may be obtained if indicated)	X (may be obtained if indicated)
Height and Weight	X	X ^{†*}												
Physical Examination ³	X	X ^{†*6}		{X}	{X} [†]		{X}	{X}			{X}		{X}	{X}

Study Visit	V00	V01	V02	V03	V04	V05	V06	V07	V08	V09	V10	V11	Early Term	Unscheduled
Study Day Post 1st Vaccination	Screen Optional D-28 to -1	Dose 1 D1	D4 ±1d	D8 +2d	D22 +7d	D25	D29	D43	D82	D142	D202	D387		
Study Day Post 2nd Vaccination					Dose 2 D1	D4 ±1d	D8 +2d	D22 +7d	D61 ±7d	D121 ±14d	D181 ±14d	D366 ±14d		
Serum or Urine Pregnancy Test	X [^]	X ^{†^}			X ^{†^}									
Venous Blood Collection for Clinical Safety Laboratory Evaluations		X ¹		X ¹	X ¹		X ¹						X (if within 7 days after the last study vaccination)	X (if indicated)
Venous Blood Collection for Immunogenicity Assays		X [†]		X	X ^{†ψ}		X	X			X ^ψ		X (if within 21 days after last study vaccination)	X (if prior to 21 days after last study vaccination)
Serum Sample Collected for Future Research ⁴		X [†]		X	X [†]		X	X			X		X(if within 21 days after last study vaccination)	X(if prior to 21 days after last study vaccination)
Enrollment in AdvantageEDC SM and Randomization		X [†]												
Pre-Administration Reactogenicity Assessments		X [†]			X [†]									
Study Vaccination		X			X									
20-minute Evaluation After Study Vaccination		X			X									
Examine Study Vaccination Site		X		X	X		X						X (if within 7 days after last study vaccination)	X (if within 7 days after last study vaccination)

Study Visit	V00	V01	V02	V03	V04	V05	V06	V07	V08	V09	V10	V11	Early Term	Unscheduled
Study Day Post 1st Vaccination	Screen Optional D-28 to -1	Dose 1 D1	D4 ±1d	D8 +2d	D22 +7d	D25	D29	D43	D82	D142	D202	D387		

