4.4.5. Selection and Timing of Dose for Each Subject

Each subject is to be randomly assigned to a study group which will define the A/H7N9 vaccine dose and receipt of adjuvant for both planned study vaccinations. The first vaccination takes place on the day of randomization, and the second vaccination takes place approximately 21 days after the first vaccination (protocol defined window of 21-28 days post first vaccination).

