6.3.3. Per-Protocol Population

The Per-Protocol (PP) population includes all subjects in the mITT subset with the following exclusions:

- Data from all available visits for subjects found to be ineligible at baseline.
- Data from all visits subsequent to major protocol deviations, such as:
 - Second study vaccination not received,
 - Second study vaccination received out of window,
 - Receipt of non-study licensed live vaccine within 30 days before or after each study vaccination,
 - Receipt of non-study licensed inactivated vaccine within 14 days before or after each study vaccination,
 - Receipt of immunosuppressive therapy (e.g., corticosteroids) within 30 days before or after each study vaccination.
- Data **from** any visit that occurs out of window:
 - Visit 3 data collected before 6 days or after 10 days post first study vaccination
 - Visit 4 data collected before 20 days or after 29 days post first study vaccination.
 - Visit 6 data collected before 6 days or after 10 days post second study vaccination.
 - For subjects who did not receive the second study vaccination, visit 6 data collected before 27 days or after 31 days post first study vaccination.
 - Visit 7 data collected before 20 days or after 29 days post second study vaccination.
 - For subjects who did not receive the second study vaccination, visit 7 data collected before 41 days or after 50 days post first study vaccination.

- Visit 10 data collected before 165 days or after 195 days post second study vaccination.
- For subjects who did not receive the second study vaccination, visit 10 data collected before 200 days or after 216 days post first study vaccination.

For analyses using the PP population, subjects will be grouped based on study vaccinations received.

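### The Early Termination visit stops collecting antibody samples, safety labs and diary data before the visit windows it overlaps have closed, including 7 of the 8 days of the primary Visit 07 window

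*Protocol*

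**What the plan says.** Protocol 5.2.1 encourages subjects who withdraw to complete the Early Termination visit, and 6.4.3 lists what is done there. Three items carry a time limit counted from the last vaccination:

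- Antibody blood: "Approximately 10 mL of venous blood will be collected for serum antibody assays (if within 21 days after the last study vaccination".
- Diary: "Memory Aid information will be reviewed with subjects (if within 7 days after the last study vaccination".
- Safety labs: also limited to 7 days.

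Appendix A and SAP Table 3 repeat these limits.

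The scheduled visits have windows of their own in protocol 6.4.1. For Visit 07 (Day 43, the primary immunogenicity time point) it is "Window: Day 22+7 days post second study vaccination". For Visit 06 it is "Window: Day 8±2 days post second study vaccination", and Visit 03 has the same form after dose 1. For Visit 10 it is "Window: Day 181±14 days post second study vaccination".

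For the per-protocol population, SAP 6.3.3 removes "Visit 7 data collected before 20 days or after 29 days post second study vaccination". Anything from 20 to 29 days is therefore kept.

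Protocol 7.2.2 says that sera available from early withdrawals will be assayed. Protocol 10.5.4 and SAP 6.5 rule out imputation.

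**The concern.** The Early Termination visit is the last contact at which primary data can be collected from a subject who leaves. Its cut-offs are fixed numbers of days and are not tied to the scheduled visit that the subject has not yet had. If the cut-off falls before the scheduled window closes, there are days on which the analysis would accept a sample or safety result that the termination checklist does not ask for.

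Three primary endpoints are touched: Day 43 antibody response, solicited reactions through 7 days, and laboratory adverse events through about 7 days. With no imputation, an item not collected at termination stays missing.

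**Working it through.** **Step 1: day count.** Vaccination is Day 1, so Day k is k − 1 days after it. Day 22+7 is Day 22 to Day 29, that is 22 − 1 = 21 to 29 − 1 = 28 days after. SAP 4.4.5 gives the same range for the second-vaccination visit, which uses the same notation: "protocol defined window of 21-28 days post first vaccination". Visit 07 applies it relative to dose 2.

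**Step 2: overlap of each window with the Early Termination (ET) limit.** All figures are days after the relevant vaccination.

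| Item and visit | ET limit | Scheduled window | Covered | Uncovered |
|---|---|---|---|---|
| Antibody, Visit 07, protocol 6.4.1 | 0–21 | 21–28 (8 days) | 21 | 22–28 (7 of 8) |
| Antibody, Visit 07, SAP 6.3.3 | 0–21 | 20–29 (10 days) | 20, 21 | 22–29 (8 of 10) |
| Diary and labs, Visits 03/06, protocol 6.4.1 (Day 8±2) | 0–7 | 5–9 (5 days) | 5, 6, 7 | 8, 9 (2 of 5) |
| Diary and labs, Visits 03/06, Appendix A (Day 8+2) | 0–7 | 7–9 (3 days) | 7 | 8, 9 (2 of 3) |
| Antibody, Visit 10 (exploratory) | 0–21 | 166–194 (29 days) | none | 29 of 29 |

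Protocol 6.4.1 and Appendix A disagree on the lower end of the Visit 03/06 window and should be reconciled. The upper end is Day 10 in both, so the uncovered days are the same.

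**Step 3: what the text gives a leaver.** Take a subject who withdraws 25 days after dose 2 with Visit 07 not yet done. Section 5.2.1 points to the ET visit, where the draw condition (21 days) has lapsed. No passage tells the site to carry out Visit 07 instead. The SAP would keep a result from day 25 if it counted as Visit 7 data, but it has no rule saying that an ET sample does.

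Now take a subject who withdraws on day 8 or 9 after a dose with Visit 03 or 06 outstanding. The diary has just been completed, since it runs through 7 days, but ET review and labs have closed.

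**Step 4: size.** The plan's allowance reproduces: 106 × 0.95 = 100.7 and 53 × 0.95 = 50.35, against the assumed 100 and 50. The documents do not say how many subjects would leave on the uncovered days, so I assume two or five lost per adjuvanted arm. I use a pooled z test in place of the plan's likelihood ratio test. For the 0.50 versus 0.70 row of protocol Table 10, power is 0.828 at n = 100, 0.820 at 98 and 0.808 at 95. Across the six rows the fall is 0.007 to 0.008 for two subjects and 0.019 to 0.021 for five. These losses would draw on the existing margin of 106 − 100 = 6 per adjuvanted arm.

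**Step 5: two side inconsistencies.** For Unscheduled visits, section 6.5 allows the antibody draw up to and including 21 days, while Appendix A has "X (if prior to 21 days after last study vaccination", as does SAP Table 3. In the text available, Appendix A has no entry for AE Assessment under Early Term, while 6.4.3 requires adverse events to be recorded there and SAP Table 3 marks them.

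**The case against.** The strongest reply is that 6.4.3 lists what will be done and forbids nothing. A subject who attends 22 to 28 days after dose 2 is inside the open Visit 07 window, where 6.4.1 already calls for the draw. A sensible site would complete Visit 07 and then record the termination. Loss requires four things together: exit in a seven-day span, Visit 07 not done, a visit attended, and a site that runs only the ET list. This stands as a limit on how often data will be lost. It does not remove the mismatch, because 5.2.1 directs the subject to the ET visit and the protocol never states the substitution.

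For the diary, the phone review about 3 days after each dose has normally captured the early entries. Missed safety assessments trigger repeated contact attempts (5.2.1). Memory Aids are source documents, and SAP 9.3.1 counts a subject at the highest severity among non-missing data. All of this stands. What remains at risk is the later part of the diary.

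Several stronger readings are tempting, and the documents do not support them:

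- **Unscheduled visits also lose primary data.** Those visits do not end participation, their procedures are optional, and their labs are done if indicated with no day limit.
- **The Visit 10 gap is a primary-endpoint loss.** Day 202 responses are exploratory.
- **The 5% in protocol 10.2 counts early leavers.** It covers every exclusion from the primary analysis.
- **The lost samples bias the comparison between arms.** A subject 22 days past dose 2 is 22 − 7 = 15 days beyond the solicited period, and no passage links leaving then to reactions or to arm.

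**Conclusion.** The point holds in a narrow form. The ET antibody draw closes before 7 of the 8 protocol days for Visit 07 (8 of the 10 days that the SAP keeps). ET diary review and safety labs close before days 8 and 9 of the Visit 03/06 window. Followed as written, the text loses a primary-endpoint sample or safety result that the analysis could have used.

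This rests on two conditions: the scheduled visit has not been done, and the site applies the ET list without adding to it. The number of subjects cannot be derived from the documents and is likely to be small. No power, precision or sample-size figure needs correction. The reason to act is that the loss is avoidable at almost no cost.

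**What to change.** 1. In protocol 6.4.3, Appendix A and SAP Table 3, add a rule tied to the visit replaced. If the window of Visit 03, 06 or 07 is open and its antibody sample, safety labs or Memory Aid review is outstanding, that item is done at the ET visit. Visit 10 can be included for the exploratory durability endpoint.
2. Collect any completed Memory Aid that has not been reviewed when the subject attends the ET visit.
3. In SAP 6.3.3, state that an ET sample drawn inside a visit's per-protocol window is analysed as that visit, for example as Day 43. Without this, the extra draw does not secure the endpoint.
4. Reconcile the 21-day limit for Unscheduled visits between section 6.5 on one side and Appendix A and SAP Table 3 on the other. Reconcile the AE Assessment row of Appendix A with 6.4.3.

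The cost is document wording and, in a few subjects who are already attending, at most one 10 mL draw per outstanding sample and one diary review.

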6.5 Unscheduled Visit (if needed)

Unscheduled visits may occur at any time during this trial. Any of the following activities may be performed:

- Interim medical history, including an assessment for new medical conditions and symptoms suggestive of PIMMCs, will be obtained by interview of subjects and any changes since the previous clinic visit or contact will be noted (if indicated).
- Memory Aid information will be reviewed with subjects (if within 7 days after the last study vaccination).
- All concomitant medications will be recorded on the appropriate data collection form (if within 180 days after the last study vaccination). Receipt of any non-study influenza vaccine, including those that are experimental, what type (inactivated or live attenuated), what subtype (e.g., A/H3, A/H5, A/H9) and approximate date of vaccination will be recorded on the appropriate DCF, if known and not previously collected will be recorded if within 180 days after the last study vaccination.
- Unsolicited non-serious AEs will be documented and reported from the time of each study vaccination through approximately 21 days after each study vaccination. SAEs, MAAEs, including NOCMCs, and PIMMCs will be documented and reported from the time of the first study vaccination through approximately 12 months after the last study vaccination.
- Vital signs, including oral temperature, pulse, and blood pressure, may be obtained if indicated. Subjects must not eat or drink anything hot or cold, or smoke within 10 minutes prior to taking oral temperature.
- A targeted physical examination, including an assessment for signs suggestive of PIMMCs, may be performed, if indicated based on review of interim medical history, by a study clinician licensed to make medical diagnoses and listed on the Form FDA 1572 as the site PI or sub-investigator.
- The study vaccination site will be examined (if within 7 days after the last study vaccination).

- Post-administration reactogenicity assessments will be performed (if within 7 days after the last study vaccination).
- Approximately 10 mL of venous blood will be collected for serum antibody assays (if within 21 days after the last study vaccination).
- Approximately 10 mL of venous blood will be collected for clinical safety labs (WBC, Hgb, PLT, ALT, T. Bili, and Cr), and performed by the central (clinical) laboratory if indicated.
- Approximately 10 mL of venous blood will be collected for future research from subjects who consent to collection of serum for future use (if within 21 days after the last study vaccination) either by signing an ICF that includes collection of future use samples as a condition of study participation or by indicating that they can opt in to sample collection for future use if the ICF allows the option to choose that option.

